8.2.2 Efficacy Assessments

Radiological Imaging Assessment

The extent of disease will be evaluated by contrast-enhanced MRI/computed tomography (CT) according to RECIST version 1.1 (Section 11.8). All radiological imaging will be performed as indicated in the Site Imaging Manual provided by the

central imaging core laboratory. In order to reduce radiation exposure for subjects, low-dose CT should be utilized whenever possible.

The screening scans must be performed within 28 days prior to enrollment and will be used as baseline. All subsequent scans will be performed in the same manner as at screening, with the same contrast, preferably on the same scanner. Radiological assessment must include MRI/CT of the chest, abdomen and pelvis, as well as assessment of all other known sites of disease as detailed within the Site Imaging Manual (refer to separate Brain MRI section for details regarding MRI of the brain).

The same imaging modality, MRI field strength and IV and oral contrast agents should be used at screening should be used for all subsequent assessments. Liver specific MRI contrast agents should not be used. To reduce potential safety concerns, macrocyclic gadolinium contrast agents are recommended per National Health Institute guidelines or follow local standards if more rigorous.

During treatment and follow-up radiological imaging of the chest, abdomen, pelvis, as well as all other known sites of disease, will be performed independent of treatment cycle every 6 ± 1 weeks for the first 4 response assessments, with the first post-baseline scan to occur 6 ± 1 weeks after cycle 1 day 1. After four 6-week response assessments, radiological imaging and tumor assessment will be performed every 12 ± 1 weeks. Radiologic imaging and tumor assessment will be performed until disease progression, start of new anticancer treatment, death, withdrawal of consent or until end of study. Imaging may also be performed earlier/more frequently if clinically necessitated at the discretion of the managing physician. Radiographic response (complete response [CR], PR) requires confirmation by a repeat scan at least 4 weeks after the first documentation of response and may be delayed until the next scheduled scan to avoid unnecessary procedures. The minimum time interval for determination of stable disease is ≥ 5 weeks.

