Not all evaluated	No	NE
Unequivocal PD	Yes or No	PD
Any	Yes	PD

CR = complete response; PD = progressive disease.

^a "Non-CR/non-PD" is preferred over "SD" for non-target disease since SD is increasingly used as endpoint for assessment of efficacy in some trials, so to assign this category when no lesions can be measured is not advised.

Overall Response: Confirmation of Complete Response (CR) and Partial Response (PR) required

Overall Response First Time Point	Overall Response Second Time Point	Best Overall Response
CR	CR	CR
CR	PR	SD, PD or PRª
CR	SD	SD provided minimum criteria for SD duration met, otherwise, PD
CR	PD	SD provided minimum criteria for SD duration met, otherwise, PD
CR	NE	SD provided minimum criteria for SD duration met, otherwise, NE
PR	CR	PR
PR	PR	PR
PR	SD	SD
PR	PD	SD provided minimum criteria for SD duration met, otherwise, PD
PR	NE	SD provided minimum criteria for SD duration met, otherwise, NE
NE	NE	NE

CR = complete response; PD = progressive disease; PR = partial response; NE = not evaluable; SD = stable disease.

^a If a CR is truly met at first time point, then any disease at a subsequent time point, even disease meeting PR criteria relative to baseline, makes the disease PD at that point (since disease must have reappeared after CR). Best response would depend on whether minimum duration for SD was met. However, sometimes "CR" may be claimed when subsequent scans suggest small lesions were likely still present and in fact that subject had PR, not CR at the first time point. Under these circumstances, the original CR should be changed to PR and the best response is PR.

Special Notes on Response Assessment

- Nodal lesions Lymph nodes identified as target lesions should always have the actual short axis measurement recorded, even if the nodes regress to below 10 mm on study. In order to qualify for complete response (CR), each node must achieve a short axis < 10 mm, NOT total disappearance. Nodal target lesion short axis measurements are added together with target lesion' longest diameter measurements to create the sum of target lesion diameters for a particular assessment (timepoint).

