4.2 Subgroups

Subgroup analyses for selected secondary endpoints (ORR and PFS) may be performed by cancer type (NSCLC, Colon cancer and Pancreatic cancer).

5. Definitions

AUC:

The area under the plasma drug concentration-time curve (AUC) reflects the actual body exposure to drug after administration of a dose of the drug.

Baseline:

For any variable, unless otherwise specified the baseline is the last non-missing assessment taken prior to the first administration of AMG 510 treatment. Where baseline measurements are taken on the same day as AMG 510 and no times are present, it will be assumed that these measurements are taken prior to the study specified treatment being administered.

Protocol Number: 20190147

Date: 17FEB2022 Page 10 of 28

Baseline ECG Values in Triplicate:

The mean of the three triplicate ECG results should be calculated for baseline. If fewer than three triplicate ECG results are available, the mean of available triplicate should be calculated. For all post-baseline ECG, the mean of one triplicate ECG results at the same assessment will be calculated and used in the analysis. When an ECG is missing within a triplicate, all available data will be averaged for that time point.

Best Overall Response (BOR):

The best overall response for a subject is the best observed disease response per RECIST v1.1.

BOR is defined as the best response in the following order: CR, PR, SD, PD, or NE, where CR and PR require confirmation by a repeat, consecutive scan at least 4 weeks after the first documentation of response. A BOR of SD requires an on-study imaging of SD or better no earlier than 5 weeks after cycle 1 day 1, otherwise the BOR will be not evaluable (NE). Please see the details in Protocol Appendix 8 and refer Appendix A for deriving BOR calculation algorithm.

Change from Baseline:

Change from Baseline is the arithmetic difference between post-dose assessment and Baseline value.

Change (absolute) from Baseline = (Post-baseline Value - Baseline Value)

Percent Change from Baseline = [(Post-baseline Value-Baseline Value) / Baseline Value] ×100

Diseases Control Rate (DCR):

Diseases Control Rate is defined as the proportion of subjects in whom the best overall response is determined as CR, PR, or SD.

DLT:

A DLT is defined as any adverse event meeting the criteria listed in Protocol Section 6.2.2 occurring during the first treatment cycle of AMG 510 (day 1 through day 21) where a relationship to AMG 510 cannot be ruled out.

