Duration of Response (DOR):

Protocol Number: 20190147

Date: 17FEB2022 Page 11 of 28

The duration of response is defined as time from first evidence of confirmed PR or CR to disease progression or death due to any cause, whichever occurs first. DOR will be calculated only for subjects who achieve a confirmed BOR of PR or CR.

DOR (months)= (PD or death date – response start date +1) x 12 / 365.25

Subjects will be censored following the censoring strategy described in Table 5-1.

Duration of Stable Disease (DoSD):

Duration of stable disease will be measured from the start of treatment to disease progression or death, whichever occurs first. DoSD will be calculated in subjects with best overall response SD. Subjects will be censored following the censoring strategy described in Table 5-1.

End of IP Administration (End of IP Admin):

End of IP Admin for each subject is defined as the date the decision was made to end IP as recorded on the End of Investigational Product Administration CRF page.

End of Study (Individual Subject):

End of study for each subject is defined as the date the subject last completed a protocol-specified procedure. The date will be recorded on the End of Study CRF page.

End of Study (End of Trial):

The end of study date is defined as the date when the last subject across all sites is assessed or receives an intervention for evaluation in the study (ie, last subject last visit), following any additional parts in the study (eg, safety follow-up), as applicable.

Investigational Product:

The term 'investigational product' is used in reference to AMG 510.

Last Investigational Product Dose Date:

The last IP date for each subject is defined as the latest date IP administered.

Objective Response Rate (ORR):

Objective response rate is defined as the proportion of subjects with a BOR of confirmed CR or PR.

Progression Fee-Survival (PFS):

Protocol Number: 20190147

Date: 17FEB2022 Page 12 of 28

The PFS is defined as interval from the first dose of AMG 510 until disease progression or death due to any cause, whichever comes first in the absence of subsequent anticancer therapy. The censoring rules for the progression-free survival analysis are detailed in Table 5-1.

PFS (months) = (PD or death date – start of treatment date +1) x12/365.25

Table 5-1. Date of Progression or Censoring for PFS

Situation (before data cutoff/ end of	Main Analysis			
study)	Date of Event or Censor	Outcome		

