9.7 Other Analyses

9.7.1 Analyses of Pharmacokinetic or Pharmacokinetic/Pharmacodynamic Endpoints

For AMG 510, PK parameters including, but not limited to C_{max} , t_{max} , and AUC will be determined from the concentration-time profile using standard non-compartmental approaches and considering the profile over the complete sampling interval. Based on

Protocol Number: 20190147

Date: 17FEB2022 Page 23 of 28

the review of the data, analyses to describe the relationship between AMG 510 exposure and either pharmacodynamic effect and/or clinical outcome may also be performed.

10. Changes From Protocol-specified Analyses

There are no changes to the protocol specified analyses.

11. Literature Citations / References

Clopper C.J. and Pearson E.S. The Use of Confidence or Fiducial Limits Illustrated in the Case of the Binomial. Bimetrika Vol. 26., No. 4 (Dec., 1934): 404-413

Kalbfleisch, J.D. and Prentice, R.L. The Statistical Analysis of Failure Time Data, New York: John Wiley & Sons; 1980

Klein, J.P. and Moeschberger, M.L. Survival Analysis: Techniques for Censored and Truncated Data, New York: Springer-Verlag; 1997

World Health Organization 2018 Statistics. Accessed at: http://www.who.int/en/news-room/fact-sheets/detail/cancer on 01 August 2019.

Protocol Number: 20190147

Date: 17FEB2022 Page 24 of 28

12. Prioritization of Analyses

No priority of output is planned for this study.

13. Data Not Covered by This Plan

The analysis of Biomarkers and PRO endpoint is not covered in this plan.

Date: 17FEB2022 Page 25 of 28

14. Appendices

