Appendix A. BOR Calculation Algorithm

BOR by investigator (used in interim analysis) will need to be derived based on Timepoint response collected on RECIST 1.1 CRF. Table 14-1 provides the BOR determination per RECIST 1.1 for trials where response confirmation is required. A BOR determined by Table 14-1 is considered a *Confirmed_BOR*.

At interim analysis, an unconfirmed response rate may be reported in addition to the confirmed response rate. The unconfirmed rate includes subjects who achieved a PR or CR and are awaiting a confirmative scan (ie, unconfirmed responders). If these subjects have disease progression or death before the confirmative scan, then they are no longer considered as unconfirmed responder awaiting confirmative scan.

Table 14-1. BOR per RECIST 1.1

Criterion	Timepoint T1 Response	T1 ≥ 35 days after Baseline?	Timepoint T2 Response	T2 ≥ 35 days after Baseline?	T2 ≥ 28 days after T1?	BOR
C1	CR	Yes	CR	-	Yes	CR
C2			CR	-	No	SD
C3			PR, SD	-	-	Query data*
C4			PD	-	-	SD
C5			NE, No further	evaluations		SD
C6		No	CR	-	Yes	CR
C7			CR	Yes	No	SD
C8			PR, SD	-	-	Query data*
C9			PD	-	-	PD
C10			NE, No further	evaluations		NE
C11	PR	Yes	CR, PR	-	Yes	PR
C12			CR, PR	-	No	SD
C13			SD	-	-	SD
C14			PD	-	-	SD
C15			NE, No further	evaluations		SD
C16		No	CR, PR	-	Yes	PR
C17			CR, PR	Yes	No	SD
C18			SD	Yes	-	SD

Protocol Number: 20190147

Date: 17FEB2022 Page 26 of 28

C19			PD	-	-	PD
C20			NE, No further	evaluations		NE
C21	SD	Yes	CR, PR, SD, PD, NE, no more evaluation			SD
C22		No	CR, PR, SD	Yes	-	SD
C23			CR, PR, SD	No	-	NE
C24			PD	-	-	PD
C25			NE, No further	evaluations		NE
C26	PD		-			PD
C27	NE	-	NE, No further	evaluations		NE
C28		-	CR, PR, SD	Yes	-	SD
C29		-	CR, PR, SD	No	-	NE
C30		-	PD	-	-	PD

CR = complete response, PR = partial response, SD = stable disease, PD = progressive disease, and NE = not evaluable.

^{*}If a CR is truly met at first time point, then any disease seen at a subsequent time point, even disease meeting PR criteria relative to baseline, makes the disease PD at that point (since disease must have reappeared after CR). Best response would depend on whether minimum duration for SD was met. However, sometimes 'CR' may be claimed when subsequent scans suggest small lesions were likely still present and in fact the patient had PR, not CR at the first time point. Under these circumstances, the original CR should be changed to PR and the best response is PR.

Protocol Number: 20190147

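### SAP Table 14-1 allows two best responses for a claimed CR that is re-read as PR, because the footnote to rows C3 and C8 omits the confirmation condition

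*SAP*

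**What the plan says.** SAP Section 5 defines best overall response (BOR) so that "CR and PR require confirmation by a repeat, consecutive scan at least 4 weeks after the first documentation of response". The same section adds: "Objective response rate is defined as the proportion of subjects with a BOR of confirmed CR or PR". Protocol Section 8.2.2 agrees that a radiographic response "requires confirmation by a repeat scan at least 4 weeks after the first documentation of response".

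Table 14-1 in SAP Appendix A turns pairs of time point responses (T1, T2) into a BOR, and the appendix labels any BOR from that table as confirmed. In rows C3 (T1 at least 35 days after baseline) and C8 (T1 earlier), T1 is CR and T2 is PR or SD. The column headed "T2 ≥ 28 days after T1" carries a dash in both rows, and the result is a data query with a footnote.

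The footnote gives two outcomes. If the CR was real, disease at T2 is progression and BOR depends on the minimum SD duration. If the CR was miscalled because small lesions were probably still present, then "Under these circumstances, the original CR should be changed to PR and the best response is PR".

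Protocol Appendix 8 (Section 11.8) has the same footnote, but only on the row for CR followed by PR. Its row for CR followed by SD has no footnote and reads "SD provided minimum criteria for SD duration met, otherwise, PD". SAP Section 10 states: "There are no changes to the protocol specified analyses".

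**The concern.** The SAP puts PR and SD at T2 into one cell under one footnote. Taken literally, once a CR is re-read as PR the subject's BOR is PR, even if the next scan was SD or came too early to confirm anything. Elsewhere the plan scores the same corrected scans as SD. Two subjects with identical corrected scans could then get different BORs, depending only on whether T1 was first entered as CR or as PR.

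Under the literal rule the subject counts as a confirmed responder, enters the duration of response (DOR) and time to response (TTR) sets, and leaves the duration of stable disease (DoSD) set. The shift can go only towards a higher ORR, and the main efficacy analysis uses investigator readings in an open-label study.

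**Working it through.** The plan states no figure for BOR or ORR, so there is none to reproduce. The check compares rules and then sizes one reclassified subject.

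**1. Same corrected scans, three rules.** T1 was entered as CR and is corrected to PR after the query.

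| T2 as recorded | T1 to T2 | Footnote, literal | Table 14-1 PR rows | Protocol Appendix 8, CR then T2 |
|---|---|---|---|---|
| PR | at least 28 days | PR | PR (C11, C16) | SD, PD or PR, by footnote |
| PR | under 28 days | PR | SD (C12, C17) | SD, PD or PR, by footnote; no interval stated |
| SD | any | PR | SD (C13, C18) | SD if minimum SD duration met, otherwise PD; no footnote |

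The rules agree only in the first line. Rows C17 and C18 also need T2 at least 35 days after baseline. If both scans are earlier than that, a corrected pair with T2 = SD, or with T2 = PR under 28 days, matches no row.

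**2. Can SD follow such a T1?** Appendix 8 defines PR as a fall of at least 30% in the target sum from baseline, and PD as a rise of at least 20% and 5 mm over the smallest sum. SD at T2 therefore means a sum above 0.70 × baseline. For T2 to stay under the 20% limit, the re-read T1 sum must be at least 0.70 / 1.20 = 0.58 of baseline. Otherwise only the 5 mm limit can prevent PD, which needs very small lesions. Example with assumed sizes: baseline 60 mm and a T1 residual of 10 mm. SD at T2 means more than 0.70 × 60 = 42 mm, a rise of more than 32 mm (320%), which is PD. So most recorded CR-then-SD pairs should become PR then PD when T2 is re-checked (C14 gives SD, C19 gives PD).

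**3. Can the interval be under 28 days?** Protocol Section 8.2.2 schedules the first four response assessments every 6 ± 1 weeks. With windows counted from cycle 1 day 1 (an assumption), the closest first and second scans are (12 − 1) × 7 − (6 + 1) × 7 = 77 − 49 = 28 days apart. A shorter gap needs an unscheduled scan, which that section allows, or the end-of-treatment scan for subjects who stop for a reason other than progression.

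**4. Size of one subject.** The shift in ORR is 1/n: 1/6 = 16.7 points, 1/12 = 8.3 points, 1/18 = 5.6 points. Illustration with assumed counts and Clopper-Pearson 95% intervals at n = 12: 3/12 = 25.0% (5.5 to 57.2) becomes 4/12 = 33.3% (9.9 to 65.1). The disease control rate (DCR) does not change where the alternative to PR is SD, because both count.

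**The case against.** The strongest reply is that the table assigns no BOR here. Rows C3 and C8 call for a query. Once T1 is corrected to PR on the CRF, the record belongs to rows C11 to C20, and the Section 5 confirmation rule applies. A programmer who works that way gets SD. This stands as a legitimate reading. It does not remove the problem, because the footnote goes on to state the BOR for each outcome of the query, and one stated outcome contradicts that reading.

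A reader might infer that unconfirmed responses will be counted in the confirmed ORR. The documents do not support that as a certainty. Inflation follows from the literal footnote, while Section 5 points the other way.

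A reader might also infer that the SAP introduced the missing 28-day condition. It did not. The protocol footnote on CR then PR lacks it too, so for that case the Section 10 statement is accurate and the conflict is with the confirmation rule and rows C12 and C17. Only the extension to SD is peculiar to the SAP.

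The materiality objections also stand. Three things must coincide: a claimed CR, a judgement that it was miscalled, and then either SD or an early scan. Protocol Section 2.3 reports 13 PR and mentions no CR among 55 evaluable subjects in the global study. Central-review sensitivity analyses and subject listings could bring such a case to light. With fewer than 10 subjects, listings may replace the exact interval.

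**Conclusion.** The point holds as an ambiguity with a one-sided effect. For a CR re-read as PR, the SAP supports two BORs from the same data. With SD at T2, the literal footnote departs from protocol Appendix 8 without being declared. With PR at T2 under 28 days, it conflicts with the SAP's own confirmation rule, and the protocol footnote shares the gap.

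If the literal rule is used, each affected subject adds 8.3 points to ORR at n = 12 and moves from the DoSD set to the DOR and TTR sets. DCR is unchanged, except where a T1 before day 35 would make the alternative NE or PD.

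The documents give no rate for the triggering event, which should be rare, and the responder counts used above are illustrative. ORR is secondary and no hypothesis is tested. The correction is worth making because one subject is visible in a cohort of at most 12 and the change is cheap.

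**What to change.** Replace the last sentence of the Table 14-1 footnote with wording to this effect: *T1 is corrected from CR to PR; T2 is re-checked for PD against the corrected nadir; the corrected time points are then re-evaluated under rows C11 to C20, including the 28-day condition; a pair that matches no row because both scans are less than 35 days after baseline is NE.* The NE result follows the Section 5 rule for SD that is seen too early.

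Split PR and SD at T2 into separate lines in C3 and C8, and align CR then SD with protocol Appendix 8. If the query upholds the CR, code T2 as PD and take BOR from C4 or C9, which give SD or PD as Appendix 8 does. Use the T2 date as progression for PFS, and for DoSD when BOR is SD. DOR does not apply, because such a subject is not a confirmed responder.

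Add the interval condition to the protocol footnote at its next amendment, or record the difference in SAP Section 10.

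The cost is one footnote sentence, two table rows and a small change to the BOR program, with no new data. The only downside is that ORR may be slightly lower.

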Appendix B. Handling of Dates, Incomplete Dates and Missing Dates

Below imputation rules will be used to impute start date and stop date of AE,

Concomitant Medication. Date of prior anti-cancer therapy, PD-1, PD-L1 and metastasis will be imputed using the same rule when only the date is missing (no imputation when month or year is missing).

The reference date for the following rules is the date of first dose of AMG 510.

Imputation Rules for Partial or Missing Stop Dates

	Stop Date							
		Complete: yyyymmdd		Partial: yyyymm		Partial: yyyy		
Start Date		< 1 st Dose	≥ 1 st Dose	< 1 st Dose yyyymm	≥ 1 st Dose yyyymm	< 1 st Dose yyyy	≥ 1 st Dose yyyy	Missing
Partial:	= 1 st Dose yyyymm	2	1	N/A	1	N/A	1	1
yyyymm	≠ 1 st Dose yyyymm		2	2	2	2	2	2
Partial:	= 1 st Dose yyyy	3	1	3	1	N/A	1	1
уууу	≠ 1 st Dose yyyy		3	3	3	3	3	3
Missing		4	1	4	1	4	1	1

¹⁼Impute the date of first dose; 2=Impute the first of the month; 3=Impute January 1 of the year; 4=Impute January 1 of the stop year

Imputation Rules for Partial or Missing Stop Dates

Initial imputation

- If the month and year are present, impute the last day of that month.
- If only the year is present, impute December 31 of that year.
- If the stop date is entirely missing, assume the event or medication is ongoing.

If the imputed stop date is before the start date, set stop date to missing.

If the imputed stop date is after the EOS/death date, impute as EOS/death date.

If a partial or complete stop date is present and the 'ongoing' or 'continuing' box is checked, then it will be assumed that the AE or con-med stopped and the stop date will be imputed, if partial.

Note: For subjects who were never treated (first dose date is missing), partial start dates will be set to the first day of the partial month or first day of year if month is also missing.

Protocol Number: 20190147

Date: 17FEB2022 Page 28 of 28

Appendix C. Analyte Listing

Local Laboratory						
Chemistry	Hematology	Coagulation	Lab parameter for shift tables			
Sodium	RBC	PT or INR	Albumin			
Potassium	Hemoglobin	aPTT	Alkaline Phosphatase			
Chloride	Hematocrit	Fibrinogen	Activated partial			
Bicarbonate	MCV	(optional)	thromboplastin time			
Total protein	Platelets	D-Dimer	Bilirubin			
Albumin	Calculated absolute	(optional)	Calcium Corrected			
Calcium	neutrophil count		Creatine Kinase			
Magnesium	(derived)		Creatinine			
Phosphorous	WBC		Fibrinogen			
Glucose	Differential		Glucose			
BUN or urea	Total neutrophils		Hemoglobin			
Creatinine	 Eosinophils 		Potassium			
Total creatine kinase	 Basophils 		Lymphocytes			
Total bilirubin	 Lymphocytes 		Magnesium			
Direct bilirubin	 Monocytes 		Sodium			
ALP			Neutrophils			
AST(SGOT)	Urinalysis		Platelets			
ALT(SGPT)	Specific gravity		Protein			
Glomerular filtration	pH		Aspartate			
rate (derived)	Blood		Aminotransferase			
	Protein		Alanine Aminotransferase			
TSH	Glucose		Leukocytes			
Total T3 (or free T3	Bilirubin					
per local standard)	Ketones					
Free T4	Sodium (optional)					
Total cholesterol	Potassium (optional)					
LDL						
HDL Totalesa a sida a	Microscopic exama:					
Triglycerides	Cellular casts					
	Granular casts					
	Hemoglobin casts					
	Hyaline casts					
	Mixed casts					
	WBC					
	RBC					
	Epithelial cells Bastaria					
	Bacteria					
	 Urine casts 					

ALP = alkaline phosphatase; ALT = alanine aminotransferase; aPTT = partial thromboplastin time; AST = aspartate aminotransferase; HepBsAg = hepatitis B surface antigen; HepCAb = hepatitis C antibody; HDL = high density lipoprotein; Hep = hepatitis; INR = international normalized ratio; LDL = low density lipoprotein; PT = prothrombin time; PTT = partial thromboplastin time; RBC = red blood cell count; T3 = triiodothyronine; T4 = thyroxine; TSH = thyroid stimulating hormone; WBC = white blood cell count.

Note: For creatinine clearance calculation, Modification of Diet in Renal Disease formula should be used: GFR (mL/min/1.73 m2) = 175 x SCr (mg/dL)-1.154 x age-0.203 x 0.742 (if female) x 1.21 (if African American) x 0.763 (if Japanese) x 1.233 (if Chinese).

^aMicroscopic exam to be performed at the discretion of the investigator.
